2. LIST OF ABBREVIATIONS

Abbreviation	Definition
5-HT4	5-Hydroxytryptamine 4
AE	Adverse event
AEMPS	Agencia Española del Medicamento y Productos Sanitarios
ATC	Anatomical therapeutic chemicals
BIFAP	Base de datos para la investigación Farmacoepidemiológica en Atención Primaria
CD-ROM	Compact disk-read only memory
CPRD	Clinical Practice Research Datalink
CSD	Cegedim Strategic Data
DUS	Drug utilisation study
DVD	Digital versatile disk
EMA	European Medicines Agency
EMR	Electronic medical records
ENCePP	European Network of Centres for Pharmacoepidemiology and Pharmacovigilance
EU	European Union
GP	General practitioner
GPRD	General Practice Research Database
HES	Hospital Episode Statistics
IACS	Instituto Aragonés de Ciencias de la Salud
IBD	Inflammatory bowel disease
IBS	Irritable bowel syndrome
IBS-C	IBS predominately with constipation
IBS-D	IBS predominately with diarrhoea
IBS-M	IBS predominately with mixed bowel habits
ICD-10	International Classification of Diseases and Related Health Problems (10th revision)
ICD-9	International Classification of Diseases and Related Health Problems (9th revision)
ICD-9-CM	International Classification of Diseases and Related Health Problems (9th revision) Clinical Modification
ICH	International Conference on Harmonisation
ICMJE	International Committee of Medical Journal Editors
ISPE	International Society for Pharmacoepidemiology
IT	Information Technology
MedDRA	Medical Dictionary for Regulatory Activities
N/A	Not applicable
NOS	Not otherwise specified (or unspecified)
OPCS	Operating procedure code supplement
OTC	Over the counter
PAS	Post-authorisation study
PASS	Post-authorisation safety study
PCP	Primary care physician

Abbreviation	Definition
PDR	Prescribed Drug Register
PSUR	Periodic Safety Update Report
QPPV	Qualified person for Pharmacovigilance
R&D	Research & Development
RMP	Risk management plan
STROBE	Strengthening the reporting of observational studies in epidemiology
TBD	To be determined
THIN	The Health Information Network
UK	United Kingdom
UTS	Up to standard
WHO	World Health Organization

4.5. Population

New users of linaclotide with at least 12 months of previous enrolment in the database (baseline period) before the date of first prescription or dispensation of linaclotide (index date) from three different countries: the UK, Spain, and Sweden. One cohort per country will be extracted.

4.6. Variables

The variables assessed will be age, gender, diagnosis of IBS and type (when available), pregnancy and breast-feeding (when available), diagnosis of chronic constipation, mechanical gastrointestinal obstruction or Inflammatory Bowel Disease (IBD), comorbidities, concomitant medications in addition to linaclotide, history of digestive surgery (especially history of cholecystectomy), visits/referrals to gastroenterology clinic, and bacterial/viral/parasite lab information.

All variables will be identified from electronic medical records using a pre-specified list of diagnostic, procedure, and drug codes.

4.7. Data Sources

The feasibility of conducting this utilisation study was assessed in the countries of interest and the most suitable databases identified that will be used in this study are the following three:

1. UK: the Clinical Practice Research Datalink (CPRD)

It contains information recorded by general practitioners (GPs) as part of their routine clinical practice and covers approximately 8% of the UK population. Core data include information on socio-demographic characteristics, diagnoses, symptoms, referrals, tests ordered, some test results, prescriptions issued, and additional clinical information. Prescriptions as prescribed by the primary care physician (PCP) or GP have fields for strength and dose. Medical data are coded using the Read coding system and, when linked to secondary care data from the Hospital Episode Statistics (HES), hospitalisation reasons for admission are coded by the International Statistical Classification of Diseases and Related Health Problems, 10th revision (ICD-10) and hospital tests and hospital procedures by operating procedure code supplement (OPCS) codes. The data available in the 2014, 12/14 static version of the database, included 474 research quality (acceptable) patients with at least one prescription for linaclotide.

2. Spain: SIDIAP

It is a primary care database that collects longitudinal data from electronic medical records (EMR) from 274 primary care centres in Catalonia since 2006, representing approximately 12% of the Spanish population. Data from primary and specialised care, hospital, and pharmacy are available, as well as patient characteristics, such as gender, date of birth, GP-diagnosed conditions, GP prescriptions, prescription dosing and size, date of prescription and dispensation, laboratory test results, other procedures, specialist referrals and diagnosis, hospital referrals, hospital procedures and discharge diagnoses, death date, and pregnancy information. GP diagnoses are coded following the ICD-10 codes, and hospital admissions following the International Statistical Classification of Diseases and Related Health Problems, ninth revision (ICD-9).

3. Sweden: the National Patient Registry (NPR) and Prescription Drug Registry (PDR)

Information on diagnoses will be obtained from the Swedish NPR, which covers all public inpatient care since 1987 and all outpatient visits since 2001. The medical data include main and up to 21 secondary diagnoses and up to 30 surgical procedures from public and private service providers (National Board of Health and Welfare (Sweden), 2012). Diagnoses are coded using ICD-10 codes and surgical procedures with the Nordic Classification of Surgical Procedures. Primary care is not yet covered in the NPR. At present, the NPR is updated once a year.

Information about treatment use will be obtained from the Swedish PDR. Its coverage is close to 100% of all prescribed medicines from both primary health care centres and outpatient specialists dispensed to the Swedish population, and information is available since July 2005 (Wettermark et al., 2007). The register contains data on the substance, brand name, formulation, and package, dispensed amount, dosage, expenditure, and reimbursement as well as date of dispensing. Dispensation of over-the-counter (OTC) medications is not included.

4.8. Study Size

Based on projected post-authorisation usage information provided by Almirall [MAH of linaclotide at the time of development of this protocol] in the linaclotide risk management plan (RMP), sales data and additional assumptions on the distribution of patients and treatment discontinuation, we estimated that by December 2016, roughly 2,674 patients using linaclotide could be captured by the proposed database in the UK, 2,407 in Spain, and 4,584 in Sweden. Overall, this represents over 9,650 patients who would have been exposed to linaclotide in the three target databases), assuming Almirall [MAH of linaclotide at the time of development of this protocol] sales forecasts are correct, and a combined exposure of approximately 4,572 patient-years. In the progress report for 2016, users of linaclotide included in each of the study database were reported to be below the targeted numbers. Following the recommendation of the PRAC rapporteur, the end of the data collection was then extended by one year until December 2017.

The extended time frame is considered adequate to achieve the estimated sample to conduct the linaclotide DUS and to allow for sufficient follow-up to assess long-term use of linaclotide and use by subgroups of interest.

4.9. Data Analyses

All analyses will be first performed separately in each of the study countries. In addition, for the primary study objectives, aggregated analyses with data from all three countries will be performed.

Baseline analyses will be conducted to characterise linaclotide users, and socio-demographic and clinical variables will be described for all users and for those subgroups of patients who were not sufficiently documented in the clinical development programme. The number and percentage of patients using linaclotide off-label will be also described.

Further, linaclotide treatment patterns will be described from index date to end of study period for linaclotide utilisation. Kaplan-Meier estimates will be used to describe time to discontinuation in the prescription or dispensation of linaclotide; and to describe switching from linaclotide to another drug used in IBS-C (laxatives, antispasmodics, prokinetics, or antidepressants). To better assess differences in time to event by the alleged reason for linaclotide prescription (IBS-C or other condition), Cox regression analysis will be employed if the proportional hazards assumption holds; if not, more complex models will be proposed, including predictor variable interactions with time.

Statistical analyses will be conducted using SAS® statistical software.

4.10. Milestones

The start of data collection was February 2013 in Sweden, May 2013 in the UK, and September 2014 in Spain, and the end of data collection has been extended to December 2017. Study progress reports will be issued when the Linaclotide Periodic Safety Update Reports (PSURs) are due (every six months for the first two years and yearly thereafter). No interim report is planned for this study, and a final report of study results is planned for December 2018.

5. AMENDMENTS AND UPDATES

Version	Date	Section of study protocol	Amendment or update	Reason
4.0	28 Apr 2015	N/A	Protocol version approved by PRAC	N/A
4.1	07 Jun 2016	Marketing Authorisation Holder	Change from Almirall to Allergan.	Change in MAH responsible for linaclotide
4.2	26 Jan 2017	Several sections in protocol abstract and main text	Timeline extended by one year and agreed with Rapporteur.	2016 progress report counts of linaclotide users lower than planned

In this version 4.2, the timelines for the study milestones have been updated to reflect one more year of data collection. The updated timelines are provided in Table 1 in the Milestones section below.

6. MILESTONES

Table 1. Milestones

Milestone	Date
Start of data collection	May 2013 (UK) September 2014 (Spain) February 2013 (Sweden)
End of data collection	Data collected up to December 2017 Effective date when data up to December 2017 can be accessed: UK: March 2018 Spain: June 2018 Sweden: August 2018 (NPR) and January 2018 (PDR)
Registration in the EU PAS register	March 2016
Study progress reports	With each PSUR
Interim reports	No
Final report of study results	December 2018

Abbreviations: EU=European Union; PAS=post-authorisation study; PSUR=periodic safety update report; UK=United Kingdom; NPR=National Patient Registry; PDR=Prescribed Drug Registry

7. RATIONALE AND BACKGROUND

IBS is a chronic, relapsing gastrointestinal condition characterised by abdominal pain, bloating, and changes in bowel habits. The first presentation of patients with IBS symptoms to a physician is usually in the 30 to 50-year age group, and there is a decrease in reporting frequency among older subjects (Drossman et al., 2002; IBS Global, 2009). Typically, women are diagnosed with IBS two or three times as often as men in most studies and all population-based studies have reported a female predominance (Keeling & Fielding, 1975; Thompson, 1984; 1997; Saito et al., 2002). Moreover, women make up 80% of the population with severe IBS (Longstreth & Wolde-Tsadik, 1993). Prevalence estimations vary with the diagnostic criteria used, and in the UK were estimated between 9.5% and 22% (Spiller et al., 2007).

IBS can be classified according to Rome III criteria, on the basis of the stool's characteristics: IBS-D; IBS-C; and IBS-M. Patients can transition among these subgroups (IBS Global, 2009). Approximately one third of IBS corresponds to IBS-D, one third to IBS-C and one third to IBS-M (Tillisch et al., 2005). When there is insufficient abnormality of stool consistency to meet the criteria for any of the above, IBS is said to be unsubtyped (Longstreth et al., 2006).

Prior IBS treatments were limited to lifestyle modifications, psychological interventions, and symptomatic treatments (e.g., laxatives, anti-diarrhoeals, and anti-spasmodic agents), or drugs unauthorised for this indication in some of the countries. In a recent review, current IBS-C treatment options showed limited efficacy, and the risk-benefit profile of early 5-Hydroxytryptamine 4 (5-HT₄) agonists restricts clinical use (Fortea et al., 2013).

The commercialisation of linaclotide (Constella[®]), a guanylate cyclase-C receptor agonist with visceral analgesic and secretory activities, was approved as the first medicine authorised for the symptomatic treatment of moderate-to-severe IBS-C in adults in the European Union (EU).

Use of linaclotide in certain population groups is not considered to be sufficiently documented in the linaclotide clinical development programme. Therefore, the use of linaclotide in the routine clinical care setting will also be investigated in specific subgroups, including the elderly population, males, pregnant or breast-feeding women, patients with specific comorbidities, and patients taking other medications. The use of linaclotide in groups with potential off-label use and with potential for abuse/excessive use is of special interest.

The proposed study will describe linaclotide utilisation among patients from three selected European countries: UK, Spain, and Sweden. This study is descriptive and we do not have an *a priori* hypothesis.

8. RESEARCH QUESTIONS AND OBJECTIVES

8.1. Research Questions

This study will address the following primary research questions:

- What are the characteristics of patients prescribed linaclotide?
- What is the extent of linaclotide off-label use with regards to its indication?

A secondary research question will be:

- What are the linaclotide prescription patterns?

All research questions will be assessed in three different countries: the UK, Spain, and Sweden.

8.2. Operational Objectives

- To describe the characteristics of patients prescribed linaclotide at time of first prescription (defined as socio-demographics, comorbidities (up to 15), co-medications (up to 15), and other potential variables of interest (up to 10))
- To also describe characteristics of patients by specific subgroups of interest (e.g., paediatric population, elderly population patients with diabetes, hypertension, or cardiovascular disease diagnostic codes, patients with codes for constipation only)
- To estimate the number and percentage of patients with the potential for linaclotide off-label use in the following groups: off-label/abuse/excessive use as a laxative due to the pharmacology of linaclotide within patients with eating disorders; off-label use in other types of constipation disorders distinct from IBS-C, particularly in the elderly population; and potential for off-label use in the paediatric population for chronic constipation.
- To describe the proportion and characteristics of patients prescribed linaclotide (overall and by alleged indication) who experience any of the following:
 - o Discontinuation of linaclotide (permanently during the observation period)
 - o Switching from linaclotide to drugs potentially also used by patients with IBS-C moderate to severe: laxatives, antispasmodics, prokinetics, or antidepressants (Hugin, 2003)
- To describe the duration of linaclotide treatment until discontinuation or switching

- To describe the effect of the indication (IBS-C diagnosis versus other) on the time from initiation of linaclotide to discontinuation or switching

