9.3.2. Variables at Baseline

Patients included in the DUS will be described according to their characteristics at index date, using data from the baseline period, from diagnoses, procedures and prescription information from each data source:

- Age (as continuous variable and categories <18, 18-65, ≥65 years)
- Gender
- Diagnosis of IBS and type ¹
- Comorbidities:
 - o Cardiovascular disorders or risk factors—i.e., cerebrovascular disease, coronary artery disease, angina, myocardial infarction, heart failure, arrhythmias, use of antiarrhythmic drugs, hyperlipidaemia, or use of lipid-lowering drugs
 - o Hypertension or use of antihypertensive drugs
 - o Diabetes
 - o Hepatic impairment
 - o Chronic kidney disease or chronic renal failure
 - o Inflammatory bowel conditions (i.e., Crohn's disease, ulcerative colitis, microscopic colitis)
 - o Mechanical gastrointestinal obstruction
 - o Any psychiatric disorder, as well as:
 - Depression diagnosis
 - Anxiety diagnosis
 - o Food intolerance (e.g., lactose)
 - o Celiac disease
 - o Cancer (e.g., colon)
 - o Bile salt malabsorption
 - o Immunodeficiency

¹ When possible, proportion of IBS-C.

- Obesity and eating disorders (anorexia nervosa, bulimia)
- Medications: the three most commonly prescribed medication groups in addition to the following, if not included (Only about half of IBS-C patients are expected to be on prescribed medication, but the majority of patients are expected to be self-treated [Wilson et al., 2004].):
 - Laxatives (i.e., bulk-forming laxatives, stimulant laxatives, faecal softeners, and osmotic laxatives) (Concomitant use of laxatives was described among one-third of the antispasmodic mebeverine users and it was associated with increased odds of hospitalisation [Goettsch WG, 2004].)
 - Antispasmodics (i.e., anti-muscarinic agents and direct-action smooth muscle relaxants)
 - Prokinetic drugs
 - Antidepressants (i.e., tricyclic antidepressants, selective serotonin reuptake inhibitors, serotonin-norepinephrine reuptake inhibitors, and monoamine oxidase inhibitors)
 - Antibiotics
 - Calcium and aluminium-containing antacids
 - Magnesium-containing antacids
 - H2 blockers
 - Proton pump inhibitors
 - Analgesic drug classes:
 - Non-steroidal anti-inflammatory drugs
 - Opioids
 - Other analgesics
- Other variables:
 - History of digestive surgery (especially history of cholecystectomy)
 - Gastroenterology clinic visit (Spain and Sweden) or referral (UK)

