- Switching from linaclotide to laxatives, antispasmodics, prokinetics, or antidepressants without prescription of linaclotide: defined as a prescription of laxatives, antispasmodics, prokinetics, or antidepressants that starts while on treatment with linaclotide and continues after the date of the linaclotide discontinuation. The date of switching is the date when the new prescription of laxatives, antispasmodics, prokinetics, or antidepressants is issued followed by linaclotide discontinuation. Time to switching is the interval between the date of the first linaclotide prescription and the date of switching.

To be able to define linaclotide discontinuation and switching at the end of the study period, it is necessary to have enough study period for follow-up after the expiry of the last linaclotide prescription. This time at the end of the study corresponds to the gap tolerated between prescriptions that could occur if the patient is on treatment but also hospitalized or travelling. This grace period is defined as 2.5 times the number of days of supply of the last linaclotide prescription (the prescription duration in addition to 1.5 times the number of days of supply of the last linaclotide prescription following its expiry date) plus one additional day when a potential discontinuation (or switching) could be assessed. Patients who continue taking linaclotide will be censored at the end date of the study period for linaclotide utilisation. This has implications for the interpretation of linaclotide treatment duration because it is conditioned by the study length.

Switching from linaclotide requires discontinuation in the prescription of linaclotide but these patterns will be considered exclusive events and patients experiencing switching immediately after discontinuation will be allocated to switching. Time to discontinuation and time to switching to another drug are secondary endpoints for the linaclotide utilisation study.

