9.7.1. Patient Characteristics and Medical History

At linaclotide cohort entry date or index date, the socio-demographic characteristics of all linaclotide users, comorbidities, and the most relevant co-medications will be assessed by reviewing data for a minimum of 12-months prior to index date, and summary statistics will be reported with mean and standard deviation for continuous variables and number and percentage for categorical ones. The number and proportion of patients with missing data will be reported for each of the variables of interest.

Baseline characteristics will also be described in the following subgroups of patients, selected because in the clinical development programme, the use of linaclotide in these groups reflected important missing information, potential off-label use, and potential for abuse/excessive use:

- Children and adolescents (younger than 18 years of age)
- Older adult population (65 years or older)
- Pregnant or breast-feeding women

- Male patients
- Non-IBS-C patients with chronic constipation
- Patients with known or suspected mechanical gastrointestinal obstruction or IBD
- Patients with specific comorbidities (i.e., hepatic or renal impairment, cardiovascular diseases and associated risk factors, hypertension, diabetes)
- Patients with potential for abuse/excessive use—e.g., use for weight loss (patients with body mass index <20), use as a laxative (patients with codes for constipation only).

9.7.2. *Linacotide Prescription Patterns*

Linacotide treatment patterns will be assessed in the follow-up period from index date, as defined above.

The numbers and proportions of patients who experience one of the following treatment events will be reported separately:

- Discontinuation in the prescription of linacotide
- Switching from linacotide prescription to the prescription of another drug (i.e., laxatives, antispasmodics, prokinetics or antidepressants)

Switching from linacotide requires discontinuation in the prescription of linacotide but these patients will be allocated to switching so the two categories will be mutually exclusive. Kaplan-Meier estimates will be used to describe the times to first discontinuation or switching.

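### Switching is defined by drug class and timing alone, so a new antidepressant started for depression or anxiety can count as a switch to an IBS-C drug

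*Protocol*

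**What the plan says.** Section 8.2 names the outcome: "Switching from linaclotide to drugs potentially also used by patients with IBS-C moderate to severe: laxatives, antispasmodics, prokinetics, or antidepressants". Section 9.3.3 makes it operational. A switch is "defined as a prescription of laxatives, antispasmodics, prokinetics, or antidepressants that starts while on treatment", and the new drug must still be in use once linaclotide has ended. The event time is fixed in the same place: "The date of switching is the date when the new prescription of laxatives, antispasmodics, prokinetics, or antidepressants is issued followed by linaclotide discontinuation".

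Section 9.7.2 repeats the four classes as a move to "another drug (i.e., laxatives, antispasmodics, prokinetics or antidepressants". It makes switching and discontinuation mutually exclusive, with a patient who meets both allocated to switching. Section 4.9 says Kaplan-Meier estimates will be used "to describe switching from linaclotide to another drug used in IBS-C (laxatives, antispasmodics, prokinetics, or antidepressants".

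Section 9.3.2 collects depression, anxiety and any psychiatric disorder as baseline comorbidities. It describes antidepressants, as a baseline medication group, as "tricyclic antidepressants, selective serotonin reuptake inhibitors, serotonin-norepinephrine reuptake inhibitors, and monoamine oxidase inhibitors". Sections 8.2 and 9.7.2 also plan to estimate the effect of indication (IBS-C versus other) on time to discontinuation and time to switching by Cox regression.

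**The concern.** Antidepressants are prescribed for mood and anxiety disorders as well as for bowel symptoms, and the switching rule cannot tell these uses apart. The psychiatric diagnoses that the study collects do not enter the rule. A patient who starts an antidepressant for depression while on linaclotide, later stops linaclotide and stays on the antidepressant is recorded as having switched.

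Three results are exposed:

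- The switching proportion is raised and the discontinuation proportion lowered by the same patients.
- Time to switching is dated at the issue of the antidepressant, which for such a patient may have nothing to do with the end of linaclotide.
- The indication hazard ratio for switching mixes bowel-related and psychiatric events. If psychiatric prescribing is equally common in both indication groups, the ratio is pulled towards 1. If it differs, the ratio is biased in a direction that cannot be known beforehand.

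**Working it through.** **What the text fixes.** Setting the sections side by side:

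| Section | Condition on class | Condition on timing | Condition on reason for use |
|---|---|---|---|
| 8.2 | four classes, potentially used in IBS-C | none | none |
| 9.3.3 | four classes | starts on linaclotide, continues after it stops | none |
| 9.7.2 | four classes | requires linaclotide discontinuation | none |
| 4.9 | four classes, labelled as used in IBS-C | none | none |

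No section separates switches by class or plans an analysis without antidepressants. Section 9.9 discusses misclassification of IBS type and over-the-counter use, but not this. The timing rule does limit the problem: an antidepressant already established before linaclotide, or one started by a patient who never stops linaclotide, is not a switch.

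**The plan's own figure.** Section 9.5 states about 8,800 patients for a hazard ratio of 1.2, 10% of patients with the characteristic, 40% event probability, 90% power and two-sided 5% alpha. Schoenfeld's formula gives

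events = (1.960 + 1.282)² / [0.10 × 0.90 × (ln 1.2)²] ≈ 3,513, and 3,513 / 0.40 ≈ 8,783 patients.

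The stated figure reproduces and is not in dispute.

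**Effect on a hazard ratio (assumption: share m).** Let m be the share of switch events in the reference group that is unrelated to bowel treatment, and suppose such events are equally frequent in both groups (hazard ratio 1 for them). Then

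observed HR = 1.2 × (1 − m) + 1 × m = 1 + 0.2 × (1 − m).

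| m (assumed) | Observed HR | Power at 3,520 events (8,800 × 0.40) |
|---|---|---|
| 0 | 1.20 | 90% |
| 10% | 1.18 | 84% |
| 20% | 1.16 | 75% |
| 30% | 1.14 | 65% |

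The 3,520 events are the plan's figure for discontinuation or switching. If that figure covers the two outcomes together, switching alone has fewer events and lower power in every row.

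**Number of such switches (assumption: start rate).** The documents give no rate. Take 2%, 5% or 10% of users per year starting an antidepressant for mood or anxiety, the 135 treatment days per patient and year from section 9.5, 40% of starters stopping linaclotide, and every antidepressant outlasting it:

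- 0.02 × 135/365 × 0.40 × 8,800 ≈ 26
- 0.05 × 135/365 × 0.40 × 8,800 ≈ 65
- 0.10 × 135/365 × 0.40 × 8,800 ≈ 130

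These counts cannot be turned into a share of switches, because section 9.5 gives only one 40% probability for discontinuation or switching and does not say how many of those events are switches.

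**The case against.** The best defence is that this is a class-based prescription-pattern measure in a study that states it is descriptive and has no prior hypothesis. Section 8.2 is cautious and speaks only of drugs that are potentially also used in IBS-C, and even section 4.9 describes the drug and not the prescriber's motive. A reader might infer that the protocol declares every such event a change of IBS-C therapy. It does not. What remains is that the section 4.9 label drops the caution of section 8.2 and that nothing in the planned output lets a reader see the difference.

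Section 9.7.2 also allows multivariate Cox models with other baseline variables, so depression and anxiety can be covariates. That helps with differences between the groups, but covariates are chosen by Akaike's criterion, so inclusion is not assured. Adjustment also does not turn a misclassified event into a correct one, and baseline covariates miss depression that first arises during follow-up.

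A tabulation by class might be in the SAP, which Annex 1 lists and which is not at hand. The point therefore rests on the definition and label that the protocol itself fixes, not on a missing table.

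A reader might infer from the class list in section 9.3.2 that monoamine oxidase inhibitors count as switch drugs. That list belongs to the baseline variables, while section 9.3.3 says only antidepressants. Carrying the list over is plausible but not stated.

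It is also tempting to make a diagnosis-restricted switch the main endpoint. The documents do not support this as clearly better. Section 9.3.2 searches the whole medical history for prior diagnoses, so one old code could disqualify a genuine switch. Sweden, with about 47% of projected patients, has no primary-care diagnoses. The exclusion could also differ by indication.

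**Conclusion.** The concern holds in a limited form. The protocol's switching rule counts a new antidepressant started for depression or anxiety as a switch, takes that patient out of discontinuation, and does not reveal how often this happens. The switching proportion, the time to switching and the indication hazard ratio for switching are therefore partly measures of psychiatric prescribing.

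The size is unknown. A reader might want to state what percentage of switches is false, but that needs a start rate, a share of starters who stop linaclotide and a share of events that are switches. The documents give neither the first nor the last. The hazard ratios of 1.18 to 1.14 and the 26 to 130 patients above are illustrations under stated assumptions, not estimates.

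Neither primary research question is affected, and the planned 8,800 patients stands. Severity is moderate to minor.

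**What to change.** Keep the all-class definition in section 9.3.3 and make the output interpretable:

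1. In section 9.7.2, report switching separately for laxatives, antispasmodics, prokinetics and antidepressants, in each country.
2. Repeat the switching proportion, Kaplan-Meier and Cox analyses with antidepressants removed from the switch definition. Patients whose only qualifying drug was an antidepressant then count as discontinuations, and the discontinuation results are rerun to match.
3. Optionally add a further sensitivity analysis that excludes only antidepressant starts accompanied by a recorded depression or anxiety diagnosis, with a note that primary-care diagnoses are absent in Sweden.
4. In section 9.9, state that the reason for the new prescription is not known. Bring the wording of section 4.9 into line with the more cautious wording of section 8.2.

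The cost is a few extra tables and models from data already collected. The version without antidepressants omits genuine antidepressant use for IBS-C, so it should stand beside the all-class result and not replace it.
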